9.5.2 Secondary Variables

9.5.2.1 Pearl Index

The Pearl Index and corresponding 95% CIs will be presented for all subjects in the ITT Population (see Section 9.5.1 for details) including only at-risk cycles in the denominator. At-risk cycles will be defined as cycles in which no other methods of birth control (including condoms and emergency contraception) are used by the subject as confirmed in the subject diary, and the subject confirmed that sexual intercourse occurred during the cycle in the subject diary. The number of on-treatment pregnancies and at-risk cycles will be presented.

The Pearl Index and corresponding 95% CIs will be presented for subjects aged 16 to 35 years and for all subjects in the ITT Population including all cycles in the denominator with the exception of cycles after the cycle of conception in the case of pregnancy.

The Pearl Index and corresponding 95% CIs will also be presented for subjects aged 16 to 35 years and for all subjects in the ITT Population employing a modified at-risk definition. With this definition, at-risk cycles will be defined as cycles in which no other methods of birth control (including condoms and emergency contraception) are used by the subject while cycles with and without confirmed intercourse are being included in the denominator.

9.5.2.2 Method Failure Pearl Index

The method failure Pearl Index is calculated using the same method as the Pearl Index (see Section 9.5.1 for details), but includes only those pregnancies that were classified as method failure (see Section 5.9.4 for details). Pregnancies due to user failure will be excluded from the numerator.

The method failure Pearl Index and corresponding 95% CIs will be presented for subjects aged 16 to 35 years at Screening in the ITT Population and for all subjects in the ITT Population including only at-risk cycles in the denominator. The number of on-treatment pregnancies and at-risk cycles will be presented.

This will be derived in 4 ways:

- Including all at-risk cycles in the denominator where at-risk cycles will be defined as cycles in which no other methods of birth control (including condoms and emergency contraception) are used by the subject as confirmed in the subject diary and the subject confirmed that sexual intercourse occurred during the cycle in the subject diary.
- Including all at-risk cycles in the denominator employing a modified at-risk definition. With this
 definition, at-risk cycles will be defined as cycles in which no other methods of birth control
 (including condoms and emergency contraception) are used by the subject while cycles with and
 without confirmed intercourse are being included in the denominator.
- Including only at-risk cycles in the denominator where at-risk cycles will be defined as cycles in which no other methods of birth control (including condoms and emergency contraception) are used by the subject as confirmed in the subject diary and the subject confirmed that sexual intercourse occurred during the cycle in the subject diary where the subject was compliant with the dosing rules 3 to 8 in Section 5.1.1.
- Including only modified at-risk cycles in the denominator where at-risk cycles will be defined as cycles in which no other methods of birth control (including condoms and emergency contraception) are used by the subject as confirmed in the subject diary where the subject was compliant with the dosing rules 3 to 8 in Section 5.1.1 while cycles with and without confirmed intercourse are being included in the denominator.

9.5.2.3 Life-Table Rates

In addition, the cumulative pregnancy rate, as determined by life-table methods, together with the corresponding 95% CIs will be presented for all pregnancies and for all method failure pregnancies in the ITT population for all subjects and for subject's aged 16 to 35 years inclusive at Screening.

Life-table analyses will provide one-year life-table pregnancy rates for each efficacy endpoint (i.e. for all pregnancies as used in the Pearl Index and for all method failure pregnancies as used in the method failure Pearl Index). The life-table analysis will evaluate the cumulative probability of pregnancy by cycle using PROC LIFETEST in SAS where the time variable is the cycle where the estimated conception occurred for subjects who had an on-treatment event of pregnancy. Subjects who did not have an on-treatment event of pregnancy will be censored on the cycle prior to the cycle in which they discontinued from the study. The rate of pregnancy and 95% CIs will be calculated based on Kaplan-Meier estimates for each cycle. Additionally, the estimated survival function against time (cycle) will be provided.

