12.1 Determination of Sample Size

Sample size is based on needing a sufficient number of cycles such that the difference between the Pearl Index and the upper limit of the two-sided 95% confidence interval (CI) for the Pearl Index does not exceed 1. Assuming that the true Pearl Index is 1.0 and that a Poisson model is used to derive the CIs, then at least 12,337 at risk cycles are required for a power of 90% in the 16 to 35 year old population.⁸ If a not at risk cycle rate of 20% and a dropout rate of approximately 45% (assuming that we have an average of 4 cycles for subjects that discontinue) are assumed, approximately 1800 16 to 35 year old subjects need to be enrolled and initiate the investigational product. Additionally, it is planned for a maximum of 200 subjects > 35 years to be enrolled and initiate the investigational product. Therefore, in total, approximately 2000 subjects will be enrolled in the study and initiate the investigational product. Additionally, a subset of approximately 500 subjects will be enrolled in the PK Substudy.

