12.4 Efficacy Analyses

The efficacy analysis will be based on the Pearl Index. The Pearl Index, defined as the number of pregnancies per 100 women-years of treatment, will be calculated as

 $Pearl Index = \frac{1300 \times \text{number of on} - \text{treatment pregnancies}}{\text{number of women} - 28 \text{ day equivalent cycles of treatment}}$

Only at risk cycles, i.e. cycles in which no other methods of birth control (including condoms) are used and during which the subjects confirmed that sexual intercourse has occurred, will be included in the denominator of the Pearl Index calculation. The subject diary data will be used to determine whether additional birth control methods were used and whether the subject has had intercourse.

Note that if conception occurs in a cycle, then that cycle will be included in the denominator even if other methods of birth control were used during that cycle or the subject did not confirm that they had had sexual intercourse. Cycles after the cycle of conception will be excluded from the denominator. All on-treatment pregnancies will be included in the numerator for the Pearl Index.

On-treatment pregnancy is defined as pregnancy with an estimated date of conception within the on-treatment period, i.e. Day 1 to 7 days after the intake of investigational product (whether active or inactive tablet). In cases where the date of conception cannot be established unequivocally (e.g. subjects is lost to follow-up), this pregnancy will be considered an on-treatment pregnancy. For calculation purposes a cycle will be defined as 28 days.

The method failure Pearl Index is calculated using the same method as the Pearl Index, but includes only those pregnancies that were classified as method failure and not pregnancies due to user failure, i.e. incorrect intake of the contraceptive product. Compliance data will be used to determine if the pregnancy was due to user failure.

Each on-treatment pregnancy will be reviewed and classified as either a method failure or a user failure pregnancy prior to database lock. Pregnancies will only be designated as user

failures if there is documentation that the subject did not use the test article correctly during the treatment cycle the conception occurred, including the instructions to be followed in case of missed pill(s).

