12.4.2.2 Life-Table Rates

In addition, the cumulative pregnancy rate, as determined by life-table methods, together with the corresponding 95% CIs will be presented for all pregnancies and for all method failure pregnancies in the ITT population. This will be repeated for all ages and for subject's age 16 to 35 years inclusive at Screening.

Life-table analyses will provide one-year life-table pregnancy rates for each efficacy endpoint (i.e. for all pregnancies as used in the Pearl Index and for all method failure pregnancies as used in the method failure Pearl Index). The life-table analysis will evaluate the cumulative probability of pregnancy by cycle using PROC LIFETEST in SAS where the time variable is the cycle

Amendment Final Version 1.1

where the estimated conception occurred for subjects who had an on-treatment event of pregnancy. Subjects who did not have an on-treatment event of pregnancy will be censored on the cycle at which they discontinued from the study. Cumulative probabilities of pregnancy and 95% CIs will be calculated based on Kaplan-Meier estimates through Cycle 13. Additionally, the estimated survivor function against time (cycle) will be provided.

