3.1 Sample Size Considerations

Sample size is based on the need to have a sufficient number of cycles such that the difference between the Pearl Index and the upper limit of the two-sided 95% confidence interval (CI) for the Pearl Index does not exceed 1. Assuming that the true Pearl Index is 1.0 and that a Poisson model is used to derive the CIs, then at least 12,337 at-risk cycles are required for a power of 90% in the 16 to 35 year old population (Gerlinger et al., 2003).

Assuming 80% of the study cycles are at-risk cycle and a dropout rate of approximately 45% (assuming that we have an average of 4 cycles for subjects that discontinue) are assumed, approximately 1800 16-to-35 year old subjects need to be enrolled. Additionally, it is planned to enroll a maximum of 200 subjects 36-50 years. Therefore, in total, approximately 2000 subjects will be enrolled in the study. Additionally, a subset of approximately 500 subjects will be enrolled in the PK Substudy.

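### The pregnancy life table shares the Pearl Index numerator but not its at-risk restriction, and the documents do not say so; on the plan's own 20% assumption the one-year rate reads about 15% to 20% lower.

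*SAP*

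**What the plan says.** Protocol 12.4 limits the Pearl Index denominator: "Only at risk cycles, i.e. cycles in which no other methods of birth control (including condoms) are used", with confirmed intercourse as the second condition. SAP 5.1.1 and 9.5.1 repeat this, and the first of the four method-failure versions in SAP 9.5.2.2 uses the same definition. All on-treatment pregnancies enter the numerator, and a conception cycle always counts.

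For the life table, protocol 12.4.2.2 says: "The life-table analysis will evaluate the cumulative probability of pregnancy by cycle using PROC LIFETEST in SAS". The time variable is the cycle of conception, or a censoring cycle for women without an on-treatment pregnancy. The population is ITT, and no condition on contraception or intercourse is attached. SAP 9.5.2.3 has the same structure and ties the analysis to the Pearl Index in these words: "Life-table analyses will provide one-year life-table pregnancy rates for each efficacy endpoint (i.e. for all pregnancies as used in the Pearl Index".

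The censoring rules differ. The protocol censors at the cycle of discontinuation; the SAP censors at the cycle before it.

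The cumulative pregnancy rate is a named secondary efficacy variable for ages 16 to 35 and for all subjects (SAP 4.2.1).

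**The concern.** The primary result and a secondary efficacy endpoint will be read together, built from the same pregnancies but from different exposure. A woman stays in the life-table risk set through cycles in which she used condoms or had no intercourse. Those cycles add to the denominator but not to the Pearl Index exposure, so the cumulative rate comes out lower.

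Elsewhere the SAP treats the choice of denominator as material. It labels three exposure bases for the Pearl Index and four for the method-failure index. The life table has one, without a label, and it resembles the all-exposure sensitivity analysis more than the primary one. For method failure no all-exposure Pearl Index is planned (SAP 5.1.1 confines that denominator to all on-treatment pregnancies), so the method-failure life table has no Pearl Index on a matching base.

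**Working it through.** **Inputs from the documents**
- Design value: "Assuming that the true Pearl Index is 1.0 and that a Poisson model is used to derive the CIs" (SAP 3.1).
- Precision target: the difference between the Pearl Index and "the upper limit of the two-sided 95% confidence interval (CI) for the Pearl Index does not exceed 1"; "at least 12,337 at-risk cycles are required for a power of 90" per cent.
- Not-at-risk share f = 20%. Protocol 12.1 has "If a not at risk cycle rate of 20% and a dropout rate of approximately 45" per cent; SAP 3.1 has "Assuming 80% of the study cycles are at-risk cycle and a dropout rate of approximately 45" per cent.
- Women who discontinue average 4 cycles, completers have 13, and N is about 1800 for ages 16 to 35.

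**The plan's own figure.** Let X be Poisson with mean E/1300, and call a result a success if 1300 × (½χ²(0.975; 2(X+1)) − X)/E ≤ 1. Power is 89.9% at E = 12,336 and 94.0% at E = 12,337. From 12,337 it stays at or above 90% (scanned to 13,500), so the stated figure is reproduced. Expected cycles per woman are 0.55 × 13 + 0.45 × 4 = 8.95. Then 1800 × 8.95 = 16,110 cycles, of which 80% is 12,888 at risk, above the 12,337 required.

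**Size of the difference, protocol censoring.** Take a constant hazard h = PI/1300 per at-risk cycle. Because the numerators are the same, the rate per counted cycle is h(1 − f), whichever cycles the conceptions fall in.
- At-risk basis: 1 − (1 − h)^13
- All-cycle basis: 1 − (1 − h(1 − f))^13

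| PI | f | At-risk | All cycles | Shortfall |
|---|---|---|---|---|
| 1 | 10% | 0.995% | 0.896% | 10% |
| 1 | 20% | 0.995% | 0.797% | 19.9% |
| 1 | 30% | 0.995% | 0.698% | 30% |
| 3 | 20% | 2.959% | 2.374% | 19.8% |
| 5 | 20% | 4.886% | 3.927% | 19.6% |

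**SAP censoring.** Dropping the discontinuation cycle of non-pregnant dropouts removes about 0.45 of 8.95 cycles per woman and leaves 8.50. As a rough check at f = 20%: 0.8 × 8.95/8.50 = 0.842, about 16% lower.

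A product-limit calculation needs dropout timing, and the documents give only the mean of 4 cycles. I assumed three patterns: all at cycle 4, uniform over cycles 1 to 7, and a declining distribution with mean 3.6. I took the discontinuation cycle to be the last cycle of use and counted completers through cycle 13. With all dropouts at cycle 4 and g = 0.8/1300, the cycle-4 risk set falls to 0.55 plus the few conceptions in that cycle. The rate is then 1 − (1 − g)^12 × (1 − g/(0.55 + 0.45g)) = 0.847%. The other two patterns each give 0.835%.

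| PI = 1 | SAP-rule rate | Shortfall from 0.995% |
|---|---|---|
| f = 10% | 0.939% to 0.952% | about 4% to 6% |
| f = 20% | 0.835% to 0.847% | about 15% to 16% |
| f = 30% | 0.731% to 0.741% | about 26% to 27% |

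**The case against.** The strongest reply is that this is a prespecified choice. Protocol and SAP agree that the life table runs over cycles of use in the ITT population, and the cumulative probability of pregnancy by cycle of use is a legitimate quantity in its own right. The SAP also plans an all-exposure Pearl Index (5.1.1, 9.5.2.1), which is its natural counterpart, and it tabulates and lists at-risk cycles. That stands, and it is why the remedy adds a table and a label and replaces nothing. It does not supply the missing statement of the exposure base, and it gives the method-failure life table no counterpart.

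Three stronger readings are tempting and are not supported:
- A reader might infer that every cycle is counted. Under the SAP rule the discontinuation cycle of a non-pregnant dropout is not.
- A reader might infer that the rate will be 20% too low. The 20% share is a sample-size assumption, and a shortfall of about 20% follows from it only under the protocol's censoring.
- A reader might infer that the SAP presents the life table as an at-risk rate. Its parenthesis identifies which pregnancies are events and says nothing about exposure.

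It is also fair that exposure is not the only source of disagreement: the SAP censoring raises the rate by about 5%, which offsets part of the shortfall. Finally, an at-risk life table takes on the diary's gaps. Unanswered questions make a cycle not at risk (SAP 5.15.1), while conception cycles are always kept. The Pearl Index already has that feature.

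**Conclusion.** The point holds as a mismatch of exposure that the documents do not state, in a secondary efficacy endpoint. With a Pearl Index of 1.0 and 20% of cycles not at risk, the life-table rate is about 20% below the at-risk rate under the protocol's censoring and about 15% to 16% below it under the SAP's. If 10% or 30% of cycles are not at risk, the shortfall is 10% or 30% under the protocol rule and about 4% to 6% or 26% to 27% under the SAP rule. These figures rest on a constant hazard and, for the SAP rule, on assumed dropout timing. The actual not-at-risk share is unknown at planning and could exceed 20%, since missing diary answers count towards it. Neither the primary Pearl Index nor the sample size is affected, and no formal test depends on the life table. This is an inexpensive improvement to consistency and reporting.

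**What to change.** In SAP 9.5.2.3:
1. Add a life table on at-risk cycles. For cycle k, let n_k be the women whose cycle k is at risk under 5.1.1 (conception cycles always included) and d_k the on-treatment pregnancies conceived in cycle k. The cumulative rate is 1 − ∏(1 − d_k/n_k) through cycle 13, with its 95% CI. Give it for all and for method-failure pregnancies, in ages 16 to 35 and in all subjects.
2. Keep the planned life table, label it all-exposure, and for all pregnancies show it beside the all-exposure Pearl Index.
3. Reconcile the censoring cycle between protocol 12.4.2.2 and SAP 9.5.2.3.

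The cost is some wording and a few extra tables. SAP 9.5.1 already lists at-risk cycles for each analysis, so the flags exist. The added rate will be slightly less favourable, and unanswered diary questions will remove cycles from n_k, as they already do for the Pearl Index; a footnote should say so.

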9.5.4 Early Termination Visit

[figure not shown]
A subject who desires early termination or is withdrawn from the study after the enrollment visit (Visit 2) (section 13.4) will require an Early Termination Visit.

- Any subject who contacts the study site with a desire to discontinue study participation should be instructed at each visit to contact the study staff before discontinuing the study drug to be counseled about alternative contraception to use prior to the Early Termination Visit (see Section 9.6.4.9). Study sites may provide any prescription or non-prescription contraceptive to the subject as is medically appropriate per local standard of care other than an IUD or implant. If necessary, an unscheduled visit can occur to provide contraception (see Section 9.5.5).
- A subject who presents to the study site for a scheduled visit and desires to discontinue study participation or is withdrawn from the study at that visit should be counseled about alternative contraception to use prior to the Early Termination Visit (see Section 9.6.4.9). Study sites may provide any prescription or non-prescription contraceptive to the subject as is medically appropriate per local standard of care other than an IUD or implant.
- A subject who presents to the study site for a scheduled visit who has not taken the study product for 16 days or more should have the scheduled visit procedures and the Early Termination Visit procedures completed at that time. The subject should be counseled about alternative contraception (see Section 9.6.4.9). Study sites may provide any prescription or non-prescription contraceptive to the subject as is medically appropriate per local standard of care.

The Early Termination Visit should occur between 16 and 23 days after the last investigational product intake or immediately if the investigational product was never started. The procedures listed in Visit 7 (see Section 9.5.3.5) will be performed and the End of Study Form will be completed.

Study site personnel will attempt to follow the progress of every subject admitted to the study through to study completion. If a subject fails to return for a scheduled visit, a reasonable effort should be made to contact the subject and ascertain the reason(s) for not returning. As a minimum, the site staff will contact the subject twice by phone and, if no response, will send a letter by registered mail.

Amendment Final Version 1.1

EST*w***TRA**

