5.0 Definitions

5.1 Cycle

The expected duration of a cycle is 28 days. A 28-day cycle consists of 24 days of active tablet intake followed by 4 days of inactive tablet intake and subjects who complete the study are expected to have completed thirteen 28-day cycles.

All cycles will be determined using the start dates recorded in the diaries. The first day of a cycle is the start date recorded on the diary for that cycle and the last day of a cycle coincides with the day before the start date recorded on the diary for the next cycle. However, because the last cycle of use has no start date for a following cycle, the last day of the cycle will be assumed to be the date of last dose of study medication, whether this is an active or inactive tablet. The date of last dose of study medication in the last cycle will be derived from the data collected in the diary.

If the conception is confirmed to be during a specific cycle in the narrative and this cycle is not in the diary data, then the cycle will be included as cycle in the exposure for the derivation of the Pearl Index. If the cycle in which conception occurred is not known, cycle(s) up to the one in which the positive pregnancy test occurred will be included in the exposure for the derivation of the Pearl Index.

For the analysis of bleeding data, the cycle will be shifted by 3 days with the 3 days of the next cycle included in the previous cycle. For example, in the bleeding analysis Cycle 2 will be from Day 4 of Cycle 2 to Day 3 of Cycle 3 inclusive.

The start and stop times of a cycle will be determined before determining whether the cycle is evaluable for the Pearl Index or evaluable for the bleeding data. Data review meetings may be held to determine if cycles are at-risk cycles for the Pearl Index and if they are evaluable for the bleeding analysis prior to database lock (see Section 8.3) if the classification is not clear from the data collected and the rules in the SAP.

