5.3 On-Treatment Period

For contraceptive efficacy, the On-Treatment Period is defined as the period of time between the date of first dose of study medication and 7 days after the last dose of study medication (regardless of whether this is an active or inactive table), inclusive. If the subject has a pregnancy after the first dose of study medication and prior to the last dose of study medication, the On-Treatment Period is defined as the period of time between the date of first dose of study medication and the date of the estimated date of conception, inclusive. If the subject has a pregnancy when they are still on study medication but the estimated date of conception is missing because the date was not confirmed in an ultrasound, then the cycle and day of the estimated conception that is assigned from the narrative will be used to determine the end date.

For TEAEs, the On-Treatment Period is defined as on or after the date of first dose of study medication.

For medications, the On-Treatment Period is defined as the period of time between the date of first dose of study medication and the date of last dose of study medication (regardless of whether this is an active or inactive table), inclusive.

If the subject had a period of time when study medication was not being taken between the date of first dose of study medication and the last dose of study medication, this time will still be considered to be during the On-Treatment Period.

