5.9.2 On-Treatment Pregnancies

On-treatment pregnancies are pregnancies with an estimated date of conception during the On-Treatment Period for contraceptive efficacy (see Section 5.3 for the definition of the On-Treatment Period). In cases where the date of conception cannot be established unequivocally (e.g. subjects is lost to follow up), this pregnancy will be considered as on-treatment pregnancy.

For on-treatment pregnancies, the cycle and day within the cycle of conception will be assigned based on the diary data collected and the estimated conception date. If the on-treatment pregnancy has an estimated date of conception in the 7-days after the last dose of study medication, then the cycle of conception will be the cycle in which the last dose of study medication was taken and the day of conception will be not applicable.

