5.15.5 Missing or Partial Treatment Start and Stop Dates

5.15.5.1 Missing Treatment Start and Stop Dates

If the subject has no diary data but has a pregnancy as per Principal Investigator's assessment in the pregnancy narrative that is classified as on-treatment or post treatment, then the subject will be classed as treated. The treatment start date and treatment stop date would be unknown in this situation.

In the case of post-treatment pregnancies, the cycle for censoring for the cumulative event rates for pregnancies cannot be determined and this will be missing. The subject will also consequently have no evaluable cycles for the Pearl Index. In the case of on-treatment pregnancies, the cycle of conception from the narrative will be used in the derivation of the cumulative event rates for pregnancies and in the derivation of the Pearl Index no other cycles would be included in the denominator for that subject.

When classifying concomitant, pre- and post medication and treatment emergent AEs and defining the Baseline assessments, the treatment start date will be assumed to be the first date in which the investigational product was dispensed and the treatment end date will be assumed to be the discontinuation or completion date for that subject. However, the start and stop dates for study medication will remain missing and the compliance and exposure will not be calculated. Similarly, the cycle of discontinuation of study medication cannot be determined and therefore this would remain missing for such subjects. The subject will have no evaluable cycles for the bleeding analysis.

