5.15.5.2 Partial Treatment Start Dates

If the subject has a partial start date Cycle 1, and consequently a partial start date for study medication, then the partial start date will be presented in the listing. If the date of last dose cannot be derived as a result of the partial start date, then this will be blank in the listings as the end date is unknown.

In the case of an on-treatment pregnancy, the cycle of conception will be estimated from the available data. If the subject does not have an on-treatment pregnancy, then for the cumulative event rates for pregnancy, the subject will be censored in the cycle where the last pill intake was reported per the diary data. Cycle 1 will be included in the denominator for the Pearl Index following the rules in Section 5.1.1 and will be included in the bleeding analysis following the rules in Section 5.1.2.

In this case, when classifying concomitant, pre- and post medication and treatment emergent AEs and defining the Baseline assessments, the treatment start date will be assumed to be the first date in which the investigational product was dispensed. If the treatment end date cannot be determined as a result of the partial start date, then the date of last dose will be derived for the day in the diary where the last pill is reported and by assuming that the start date is the latest possible day. For example, if the partial start date is January 2017 and the last day with a pill reported is Day 4 of Cycle 1, then the assumed start date would be 31 January 2017 and therefore Day 4 of Cycle 1 would be 3 February 2017 and this would be used as the date of last dose. The diary data for pill intake will be used to derive compliance and exposure per the rules in the SAP.

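### The SAP censors the pregnancy life table one cycle earlier than the protocol, without a reason and without dating discontinuation; with last-dose dating this biases the rate slightly upward

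*SAP*

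**What the plan says.** **Censoring rule.** Protocol 12.4.2.2 says that women without an on-treatment pregnancy "will be censored on the cycle at which they discontinued from the study". SAP 9.5.2.3 says they are "censored on the cycle prior to the cycle in which they discontinued from the study". In both documents an event is placed in the cycle of estimated conception, so only the censoring time moves.

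**Which date.** SAP 5.1 closes a woman's final cycle at her last tablet: "the last day of the cycle will be assumed to be the date of last dose of study medication". Study exit is later. Protocol 9.5.4 states: "The Early Termination Visit should occur between 16 and 23 days after the last investigational product intake". SAP 9.5.2.3 speaks of leaving the study, while SAP 5.15.5.1 uses a different term: "the cycle of discontinuation of study medication cannot be determined".

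**Events near the end of treatment.** SAP 5.3 defines the on-treatment period for efficacy as "the period of time between the date of first dose of study medication and 7 days after the last dose of study medication". For a conception in those 7 days, SAP 5.9.2 says "the cycle of conception will be the cycle in which the last dose of study medication was taken".

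**A different rule for the same rates.** Where the Cycle 1 start date is partial and there is no on-treatment pregnancy, SAP 5.15.5.2 says "the subject will be censored in the cycle where the last pill intake was reported per the diary data".

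**Completers.** SAP 9.1 puts women who did not leave early in Cycle 13, but only for the discontinuation life table. Neither SAP 9.5.2.3 nor protocol 12.4.2.2 has a sentence for completers.

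**The concern.** The two documents give different censoring cycles for a named secondary efficacy endpoint, and the SAP neither explains nor records the change.

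The consequence depends on the undated term. With last-dose dating, which uses the only final cycle that SAP 5.1 defines, the SAP rule treats the final cycle asymmetrically. Conceptions in it count as events, including those up to 7 days after the last tablet. Women who stopped in it without conceiving are removed from its risk set, and a woman who stops in Cycle 1 contributes no time at all. The denominator falls and the numerator does not, so the estimated rate rises. Two women with the same pill history would also be censored one cycle apart if one of them had an incomplete Cycle 1 start date.

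At stake is a small shift in the reported one-year pregnancy rate, and a result that depends on which document is programmed.

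**Working it through.** **Planning figures first.** The documents give no planning figure for the life table; the nearest is the at-risk cycle requirement (protocol 12.1, SAP 3.1). With the exact Poisson limits of SAP 9.5.1 and a true Pearl Index of 1.0, the power for an upper limit within 1 of the estimate is 94.0% at 12,337 cycles and 89.9% at 12,336. The stated 12,337 therefore reproduces. The plan supplies 1800 × (0.55 × 13 + 0.45 × 4) × 0.8 = 12,888. Neither figure depends on the life-table rule.

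**Inputs from the documents** (ages 16 to 35): 1800 women; 45% dropout, so 810 stoppers and 990 completers; a mean of 4 cycles in stoppers; Pearl Index 1.0; 20% of cycles not at risk. Hazard per cycle h = 0.8 × 1/1300 = 0.000615. The 13-cycle input rate is 1 − (1 − h)^13 = 0.797%.

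**Assumptions, not in the documents:** constant hazard; stopping cycles geometric (base case), uniform over Cycles 1 to 7, or all in Cycle 4; mean fraction f of the final cycle exposed, 0.5 in the base case and varied from 0.25 to 1; completers censored in Cycle 13; for study-exit dating, last tablets spread evenly over Days 1 to 28.

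**Formulas.** Expected events in cycle k = h × (women continuing + f × women stopping in k). Rate = 1 − Π(1 − events/risk set). The risk set is the women continuing past k, plus the women stopping in k with this weight:

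- last-pill cycle (the protocol rule with last-dose dating): 1
- SAP rule with last-dose dating: 0, except the women who conceive
- SAP rule with study-exit dating: the share whose exit falls in the next cycle, 16/28 = 57% to 23/28 = 82%
- protocol rule with study-exit dating: 1, with the same share carried into cycle k + 1

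**One cycle by hand** (geometric, f = 0.5, 186 women stopping in Cycle 1). Continuing: 1800 − 186 = 1614. Events: 0.000615 × (1614 + 93) = 1.05. The last-pill rule gives 1.05/1800 = 0.058%; the SAP rule with last-dose dating gives 1.05/1614 = 0.065%. The gap narrows in later cycles as fewer women stop.

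**13-cycle rates, f = 0.5 (%)**

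| Stopping pattern | Last-pill cycle | SAP, last-dose dating | Ratio | SAP, study-exit dating (57%; 82%) | Protocol, study-exit dating (57%; 82%) |
|---|---|---|---|---|---|
| Geometric | 0.7794 | 0.8159 | 1.047 | 0.7945; 0.7856 | 0.7595; 0.7513 |
| Uniform 1–7 | 0.7796 | 0.8161 | 1.047 | 0.7945; 0.7856 | 0.7596; 0.7514 |
| All in Cycle 4 | 0.7833 | 0.8220 | 1.049 | 0.7946; 0.7874 | 0.7638; 0.7588 |

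Over f from 0.25 to 1 and all three patterns, the ratio of SAP to protocol is 1.043 to 1.063 with last-dose dating and 1.037 to 1.047 with study-exit dating. Values near 1.06 arise only when all 810 women stop in Cycle 4 after a nearly full or full final cycle.

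**Women affected.** With last-dose dating, the women who contribute no time number 186 (geometric), 116 (uniform) or 0 (all in Cycle 4). With study-exit dating, the protocol wording would keep 810 × 0.571 = 463 to 810 × 0.821 = 665 stoppers at risk for one cycle after their last tablet.

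**Against sampling error.** Expected pregnancies in the base case are 9.66, so the relative standard error is 1/√9.66 = 32%. The shift is 4.7/32 = 15% of one standard error.

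**Against the input rate of 0.797%** (geometric). With f = 0.5, the SAP rule with last-dose dating is 2.4% high and the last-pill rule 2.2% low. Counting the 7 post-dose days (f = 0.5 + 7/28 = 0.75, same hazard, completers' 7 days left out) gives 0.8254% and 0.7882%, about 3.5% high and 1.1% low.

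**The case against.** **The SAP rule is coherent if study exit was meant.** Exit comes 16 to 23 days after the last tablet, so the cycle before it is the last-pill cycle for an estimated 57% to 82% of stoppers. That SAP 5.1 defines no cycle after the last dose is not decisive, because the protocol places Visit 7 in Cycle 14. The SAP change could then be a sensible correction of the protocol wording. This stands, although the remaining 18% to 43% of stoppers would still be censored a cycle early, and the SAP does not state this dating.

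**Last-pill censoring is not clearly more accurate.** With half-length final cycles and no post-dose days, the two rules err almost equally in opposite directions. With study-exit dating, the SAP rule (0.786% to 0.795%) is nearer the input rate than the last-pill rule (0.779%). This stands for that case. Once the SAP's own 7 post-dose days are counted, the last-pill rule is nearer than the SAP rule with last-dose dating.

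**The protocol leaves detail to the SAP.** Protocol Section 12 does so, and a different SAP rule is not in itself an error. That is fair. What is missing is a reason and a date.

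**A stronger reading on completers.** A reader might infer that completers would be censored in Cycle 12, leaving no non-pregnant woman at risk in Cycle 13 and no usable one-year rate. The documents do not support this. The censoring phrase concerns women who discontinued, SAP 9.1 puts the others in Cycle 13, and SAP 9.5.2.3 promises one-year rates. Even if the phrase were applied to completers by study exit, the cycle before Cycle 14 is Cycle 13. The missing sentence is a gap to close in both documents, not a failure of the analysis.

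**Conclusion.** The point holds as a minor one. The SAP departs from the protocol by one cycle, gives no reason and leaves the discontinuation date open. With last-dose dating the stated rule biases the rate upward, against the product, and conflicts with SAP 5.15.5.2. The excess over the protocol rate is about 4% to 6% in relative terms (base case 0.037 percentage points). With study-exit dating it is about 4% to 5%, and there the protocol wording is the weaker of the two. These sizes rest on the planning inputs and on the assumed hazard, stopping patterns and final-cycle lengths.

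A reader might also infer a threat to the contraceptive efficacy conclusion. The documents do not support that: the Pearl Index and its at-risk cycle requirement do not use this rule, SAP 9.0 plans no formal statistical analyses, and no threshold is attached to the life table.

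**What to change.** In SAP 9.5.2.3, censor women without an on-treatment pregnancy at the cycle of last tablet intake according to the diary. This agrees with SAP 5.15.5.2, and with protocol 12.4.2.2 when discontinuation is dated to the last dose. Add that completers are censored in Cycle 13, as in SAP 9.1. If study exit was intended, say so and record the departure from the protocol with its reason.

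The cost is one or two sentences and minor programming. There is a downside to declare: with last-dose dating, the base-case rate moves from 0.816% to 0.779%, slightly in the product's favour. It then sits about 2% below the input rate with half-length final cycles, or about 1% below when the 7 post-dose days are counted. An optional half-cycle sensitivity estimate, giving each stopper half a cycle of risk in her final cycle, would show this.
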